Pilot Arm – active arm but completed post-screening (i.e. offsite on own device)

Inferences about the effect of the Health4Her intervention completed post-screening (i.e. offsite on own device) on outcomes will be based on based on: 1) a comparison of change, in the pilot arm only, from baseline to immediate post-intervention (i.e. immediately post-randomisation) and/or 4-weeks post-randomisation, and 2) a comparison, between treatment groups (i.e. pilot arm vs control; pilot arm vs intervention; acknowledging that assignment to the pilot arm was not randomised), of change from baseline to immediate post-intervention (i.e. immediately post-randomisation) and/or 4-weeks post-randomisation. The analytic methods described above will be implemented here.

Missing data

Where appropriate, missing values will be addressed through maximum likelihood estimation (i.e. in a mixed model) or using multiple imputation.

Sensitivity analyses

Several sensitivity analyses may be performed:

- Using a per-protocol approach, defined as those who received all elements of the intervention.

- Stratified by participants based on those who: a) report drinking any alcohol in the past month, and b) are identified to be drinking at a level exceeding current national guidelines for weekly and/or single day consumption.
- Including relevant covariates (e.g. age, education, CALD, LGBTIQ+A+) as adjustments. Covariates may also be used to stratify analyses.
- Models to examine the robustness of missing data modelling decisions (e.g. including auxiliary variables in models or in complete case data).

Primary Outcome

- 1) Change in next-month drinking intentions (immediate post-intervention)

Secondary Outcomes

- 1) Change in next-month drinking intentions (4-weeks post-randomisation)
- 2) Change in intended number of standard drinks consumed over the next month (4-weeks post-randomisation)
- 3) Proportion of participants intending to reduce their next-month alcohol consumption (immediate post-intervention)
- 4) Proportion of participants intending to reduce their next-month alcohol consumption (4-weeks post-randomisation)
- 5) Proportion of participants accurately identifying alcohol as a clear risk factor for breast cancer (4-weeks post-randomisation)

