We recently completed a world-first trial (N=558), funded by VicHealth and the Eastern Health Foundation, supported by Maroondah BreastScreen (trial site) and BreastScreen Victoria, and approved by the Eastern Health Human Research Ethics Committee (LR19/011/50551), to test the effectiveness of a prototype of an electronic alcohol brief intervention (Health4Her; researcher-

administered screening alcohol questions, intervention activated by the researcher for the participant to view on an iPad alone). The electronic alcohol brief intervention model was chosen to minimise disruption to service workflow and need for human resource to implement within the busy breast screening environment. In this trial, participants reported poor alcohol literacy (4 in 5 did not have knowledge of the alcohol-breast cancer link) and a desire for more information. The Health4Her intervention was found to be highly acceptable to breast screening service consumers. For the primary outcome, there were significant increases in the proportion of participants accurately identifying alcohol as a clear breast cancer risk factor from baseline to 4-weeks in intervention (OR=41.82, 95% CI=17.76, 98.49, $p<0.001$) and control (OR=4.92, 95% CI=2.75, 8.79, $p<0.001$) arms, with a significantly greater increase in the intervention arm ($p_{\text{arm} \times \text{time}} < 0.001$) (Findings are currently under peer-review for publication). BreastScreen staff were highly supportive of the Health4Her intervention as part of routine care, however, the manually delivered intervention, dependent on dedicated human resource to administer, was considered unviable to implement in practice.

As such, the overall aim of this study is to i) collaboratively design an automated alcohol brief intervention with women who participate in breast screening, ii) examine its effects on drinking intentions and alcohol consumption among women attending breast screening service for routine mammography and iii) understand the factors affecting intervention implementation using mixed-methods program evaluation.

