Lifestyle information (control and active arm): Finalised through the collaborative design process, potential elements will be: information on physical activity and maintaining a healthy weight, which can also reduce breast cancer risk (27, 28). Post-session information will be provided via email (i.e. an electronic brochure on nutrition for maintaining a healthy weight).

Implementation evaluation of a modified active arm: This pilot group does not form part of the planned randomised controlled trial or power and sample size calculation, but is included based on findings from the previous phase of this research. A theme from the previous program evaluation was that there may be some barriers to implementing the intervention onsite in practice, due to i) women not having time to complete the intervention onsite, and ii) there being not enough space to implement the intervention at smaller services. Therefore, a small group of women (n~20) who cannot participate on the day of screening (e.g. due to other commitments, paid parking timing out, etc. as identified in the previous study) will be offered to participate in the modified active arm *offsite*. Women who agree to take part in this element of the research will access the intervention after their appointment using their personal device (e.g. computer, iPhone, iPad) and will be offered a QR code before leaving the breast screening setting and/or sent a text/email following their appointment with the link to the Health4Her-Automated platform, to receive the participant information sheet, and complete verbal consent, baseline assessment and alcohol brief intervention. While the two-arm trial remains the main focus of this study (i.e. testing the benefits of an alcohol and lifestyle brief intervention offered to women attending breast screening, which can act as a window of opportunity to increase engagement with breast cancer risk reduction information), the addition of the modified active arm will permit evaluation of this alternative implementation approach.

Power and sample size estimate:

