While this study will examine reach, uptake, feasibility and acceptability as important end-points, it will be powered to test the effectiveness of H4H-A in decreasing women's drinking intentions. The sample size has been calculated using data from a previous, related study examining the effects of alcohol warning information about the alcohol-breast cancer link on drinking intentions (15). Using a Likert 5-point response scale (1 = not at all, 5 = to a very great extent, this study showed that the warning information, *Alcohol increases your risk of breast cancer*, increased participants' intention to reduce the amount of alcohol they consume from a pre-exposure mean of 2.37 (SD = 1.18) to a post-exposure mean of 2.63 (SD = 1.22).

Given some differences in the previous study (i.e. the message about alcohol and breast cancer risk was not personally relevant to the whole sample comprising males and females 18-65 years; a single health message was provided, which is different to the Health4Her intervention containing several 'active ingredients' based on alcohol brief intervention and applied behaviour change principles), we anticipate a greater increase in participants' intention to reduce the amount of alcohol they consume in the current study. Further, based on our previous research, we anticipate some assessment reactivity among the control group.

Power and sample size estimations were conducted using General Linear Mixed Model Power and Sample Size (GLIMPSE) software. We estimate (factoring in 5% attrition, and 30% of women attending breast screening who do not drink or have not drunk in the past month) that a total sample size of at least 78 (39 per group) will have 80% power ($\alpha < 0.05$) (a total sample size of 90 [45 per group] will provide 85% power, $\alpha < 0.05$) to detect a change in women's drinking intentions of 2.37 to 3.37 (change = 1.00) in the intervention group, and a change of 2.37 to 2.63 (change = 0.26) in the control group between baseline and immediately post-intervention. Therefore, this study will aim to recruit a total

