sample size of at least 78 participants. Based on the barriers to participation and implementation identified in the previous phase of this research, the current study will provide an opportunity to collect some pilot data to inform scaled up research and implementation, to provide an indicator of outcomes for participants who complete a modified version of the alcohol brief intervention offsite using their own personal device (n~20).

Statistical analyses: A full Statistical Analyses Plan will be developed prior to trial commencement. All statistical tests will be two-tailed, with the alpha level set to 0.05 and analyses conducted using the most appropriate procedures in Stata or R. All randomised participants will be included in the analyses (i.e. intention-to-treat) for primary and secondary outcomes. Analyses will examine change in outcomes over time (baseline, immediately post-intervention, 4-weeks). For intention outcomes, we will examine differences in responses according to baseline alcohol consumption risk status (i.e. drinking at a level within/exceeding current national alcohol guidelines). For alcohol outcomes, sensitivity analyses will be performed for women who a) report drinking any alcohol in the past month, and b) are identified to be drinking at a level exceeding current national guidelines for weekly and/or single day consumption. The Generalised Linear Mixed Model approach with fixed effects for treatment and time, and their interaction, and random effects for subjects and assessments within subjects, will be applied to examine the treatment effect of the intervention on all outcomes.

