6 STUDY PROCEDURES

6.1 STUDY FLOW CHART

6.2 SCHEDULE OF ASSESSMENTS

| Assessment | Time point: | Pre-trial | Maroondah BreastScreen | | Online survey |
|--|-------------|-----------|-------------------------------------|--------------------------------------|----------------------------------|
| | | | 0 (immediately pre-intervention) | 1 (immediately post-intervention) | 2 (4-weeks post-intervention) |
| COLLABORATIVE DESIGN OF H4H-A | | | | | |
| In-person and online workshops with breast screening service consumers | | x | | | |
| IMPLEMENTATION OF H4H-A^a | | | | | |
| Eligibility assessment (breast screening staff will assess English comprehension; question about access to computer, tablet or | | | x | | |

| | | | | |
|---|--|---|-----------------------------|-------------|
| smartphone embedded at start of intervention) | | | | |
| Trial explanation (embedded at start of intervention) | | x | | |
| PIS (link embedded at start of intervention, and emailed) | | x | | |
| Informed consent (embedded at start of intervention) | | x | | |
| Randomisation | | | x | |
| Intervention | | | x | |
| Measures | | | | |
| Primary outcome | | | | |
| Drinking intentions (5-point Likert scale) | | x | x | x |
| Secondary outcomes | | | | |
| Drinking intentions (QF intentions) | | x | | x |
| Alcohol-breast cancer literacy | | x | | x |
| Alcohol literacy | | x | | x |
| Alcohol consumption (past-month QF) | | x | | x |
| Knowledge of other breast cancer risk factors | | x | | x |
| PROGRAM EVALUATION ^a | | | | |
| Trial / service administrative data collection | | | (throughout implementation) | |
| Participant feedback | | | | (end trial) |
| Site staff and manager feedback | | | | (end trial) |

^a Participants in the modified active arm being piloted will participate in eligibility assessment, informed consent, baseline, intervention, follow-up and program evaluation in the same way as participants in the active / control arms, but will not be randomised and will complete all activities offsite.

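### The SAP treats uncontrolled pre-post change in the pilot arm as evidence of the offsite version's effect, although the protocol expects change in controls too

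*SAP*

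**What the plan says.** The SAP's Pilot Arm section names two bases for inference about the effect of the offsite version. The first is "a comparison of change, in the pilot arm only, from baseline to immediate post-intervention" and/or 4 weeks. The second is a comparison of change between the pilot arm and each randomised arm, with an acknowledgement that assignment to the pilot arm was not randomised. The two are joined without ranking, and the first is not called descriptive. The section then applies the methods set out earlier in the SAP, where all tests are two-tailed at 0.05. For the randomised arms, the SAP's Analytic approach section rests inference about effect on the between-group comparison of change alone.

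The protocol describes the pilot women as those "who cannot participate on the day of screening" (section 4.2), and the footnote to section 6.2 says they "will not be randomised and will complete all activities offsite". Section 4.2 gives the purpose of these data as "to provide an indicator of outcomes for participants who complete a modified version of the alcohol brief intervention offsite".

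On change without the alcohol content, the sample size text in section 4.2 says "we anticipate some assessment reactivity among the control group" and plans for "a change of 2.37 to 2.63 (change = 0.26) in the control group". Section 2 reports that correct identification of alcohol as a clear risk factor rose in both arms of the previous trial: "and control (OR=4.92, 95% CI=2.75, 8.79", p<0.001, for controls. The same measure is secondary outcome 5 in the SAP.

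**The concern.** A pre-post comparison in one arm answers whether responses changed. It answers whether the intervention changed them only if no change would have occurred otherwise, and the protocol does not believe that. It plans for movement in women who receive no alcohol content and has already seen such movement on one of this trial's secondary outcomes. On its own planning values the active-arm change is 1.00, while the effect relative to control is 1.00 − 0.26 = 0.74. The within-arm figure is therefore 1.00/0.74 = 1.35 times the effect.

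The pilot data are meant to inform larger studies and implementation. A significant pilot-only change could be reported as an effect of the offsite version when it is no more than the change expected in controls.

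**Working it through.** **Inputs from the documents.** SDs 1.18 (pre) and 1.22 (post); planned change 1.00 (intervention) and 0.26 (control); 39 per randomised arm; 5% attrition; 30% non-drinkers; pilot n about 20 (all protocol 4.2). Previous control-arm OR 4.92, 95% CI 2.75 to 8.79, and "4 in 5 did not have knowledge of the alcohol-breast cancer link", so about 20% correct at baseline (protocol 2). Two-sided 0.05 (SAP).

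**Assumption.** The pre-post correlation ρ is not given. I use 0.7, with a range of 0.3 to 0.8.

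**Step 1: the plan's own figure.** The SD of change is √(1.18² + 1.22² − 2ρ·1.18·1.22), which is 1.420, 1.200, 0.930 and 0.760 for ρ = 0.3, 0.5, 0.7 and 0.8. With 39 × 0.95 × 0.70 = 25.9 effective women per group and a difference of 0.74, 80% power needs an SD of change of 0.951, i.e. ρ of about 0.69. At ρ = 0.7 a t-test has 80.2% power at 39 per group and 85.7% at 45, against the stated 80% and 85%. So 0.7 is consistent with the sample size, although the documents do not state it.

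**Step 2: drinking intentions, pilot-only test with no effect beyond control-type change.** Paired t-test against zero, noncentrality = change ÷ (SD/√n). At ρ = 0.7 and n = 20 this is 0.26 ÷ (0.930/√20) = 1.25. Fourteen drinkers is 20 × 0.70. Probability of a significant result:

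| True change | n | ρ=0.3 | ρ=0.5 | ρ=0.7 | ρ=0.8 |
|---|---|---|---|---|---|
| 0.26 | 20 | 0.122 | 0.151 | 0.221 | 0.306 |
| 0.26 | 14 | 0.097 | 0.117 | 0.163 | 0.221 |
| 0.13 (halved) | 20 | 0.068 | 0.075 | 0.091 | 0.112 |

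**Step 3: alcohol-breast cancer knowledge at 4 weeks.** Assumptions: 20% correct at baseline, the OR read as subject-specific, a random-intercept logistic model with SD 2 (range 0 to 3), n = 20, no attrition, and McNemar mid-p standing in for the mixed-model time contrast. Probability of significance if pilot women change only by the OR shown (100,000 simulated trials):

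| OR | SD 0 | SD 1 | SD 2 | SD 3 |
|---|---|---|---|---|
| 4.92 | 0.597 | 0.496 | 0.323 | 0.183 |
| 2.75 | 0.257 | 0.204 | 0.124 | 0.066 |
| 8.79 | 0.870 | 0.792 | 0.599 | 0.387 |
| 1 | 0.034 | 0.029 | 0.018 | 0.010 |

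If the OR is instead read as marginal, the post-intervention odds are 0.25 × 4.92 = 1.23, or 55% correct. The exact McNemar test is then significant with probability 0.49 to 0.76, depending on how individual answers switch. The 32% is the lower of the two readings' central values.

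**Step 4: is pilot versus control better?** It is imperfect too. Suppose offsite women drifted by 0.52 against 0.26 in controls (an assumption). Pilot versus control (20 vs 39) would then be significant in 17% of trials (10% to 23%) with no alcohol-content effect. Under the same drift the pilot-only test would be significant in about 67% at ρ = 0.7.

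**The case against.** The strongest reply is that the SAP asks for both comparisons. If the two bases must agree before an effect is claimed, the relevant rate is the joint one. With equal drift of 0.26 and no alcohol-content effect, both tests are significant in only about 2.4% of trials (20 vs 39). That figure is right, but it needs a rule that the SAP does not state: the section neither ranks the bases nor says what happens when they disagree. What stands is that the 22% and 32% are rates for the pilot-only test taken alone, not false-positive rates of the whole pilot analysis.

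Three further points have some weight.

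- The SAP does not spell out a within-arm test against zero. It is the natural reading of applying its two-tailed 0.05 methods to change in one arm, but an estimate with an interval would also fit the text.
- The 0.26 is a planning value. It equals the change after a warning message in the cited study and was not observed in controls. The observed control change concerns knowledge, in a trial with researcher-administered alcohol questions, and section 2 does not describe what that control arm received.
- Controls receive lifestyle content, so their change is not pure reactivity. Subtracting it isolates the alcohol content and not the whole package.

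The SAP also already plans pilot versus control and acknowledges non-randomisation. That acknowledgement belongs to the second basis and concerns selection; nothing qualifies the first. Hypothesis (i) in protocol 3.1, on knowledge of inactivity and excess weight, is a within-arm claim and is not in question here.

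**Conclusion.** The concern holds, as a minor point. The SAP places uncontrolled change under inference about effect, although the protocol's own figures show that some change is expected without the alcohol content. If pilot women changed only as planned for controls, a pilot-only test on intentions would be significant in about 22% of trials at n=20 (12% to 31%), or 16% with 14 drinkers (10% to 22%). On knowledge it would be about 32% (18% to 60%). At the limits of the OR's confidence interval, with SD 2, that becomes 12% and 60%. These figures rest on the assumed correlation, the 0.26 planning value (halving it gives 9%), and the assumed random-intercept SD and reading of the OR. The pilot is outside the randomised trial and its power calculation, so the primary comparison is unaffected.

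**What to change.** In the SAP's Pilot Arm section:

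- Report pilot-only change descriptively, as an estimate with 95% CI beside the control arm's change, and remove it as a basis for inference about effect.
- Rest any statement about the offsite effect on the pilot-versus-control difference in change, as an estimate with 95% CI.
- Keep the non-randomised caveat and say why it matters: women who could not stay on the day, and who complete everything offsite, may drift differently from onsite controls.

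This needs no new data or models, and description still meets the protocol's stated purpose for the pilot. The cost is that the pilot can no longer support a stand-alone significance claim. Under the planned effect (1.00 vs 0.26), pilot-only change would be significant while pilot versus control was not in about 19% of trials with 20 vs 39 (7% to 39%), and in 31% with 14 vs 27 drinkers at ρ = 0.7.

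The controlled estimate will also be imprecise. Its 95% CI half-width is t × SD × √(1/n₁ + 1/n₂). At ρ = 0.7 that is 0.51 for 20 vs 39 (0.42 to 0.78 over the range of ρ) and 0.62 for 14 vs 27 (0.51 to 0.95).

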1 ADMINISTRATIVE INFORMATION

1.1. TRIAL REGISTRATION

Trial to be registered with ClinicalTrials.gov, registration number: NCT06019442

1.2. EXPECTED DURATION OF STUDY

This study is expected to take 12-months to complete (6-months to complete collaborative design and automation of the Health4Her platform; 6-months to conduct the effectiveness-implementation trial, and analyse the results)

2 INTRODUCTION AND BACKGROUND

Alcohol is a major modifiable risk factor for breast cancer in women (4.4% breast cancer cases globally and 5.8% breast cancer cases in Australia are attributable to alcohol consumption) (1, 2), even in low amounts (3). Yet, population awareness of this risk remains low (<20%) (4, 5).

In Australia, per capita alcohol consumption is declining, yet risky drinking including daily drinking has remained stable among women aged 40+ years, and has even increased among those aged 50-69 years (6). While consumption earlier in life is also relevant to breast cancer development, recent intake is a determinant of breast cancer risk (7, 8), particularly after age 40 where consumption is strongly associated with breast cancer risk (7). Further, among women with a breast cancer history, alcohol intake of <1 standard drink per day is associated with an increased risk of breast cancer recurrence (9). Despite this, mid-older age women's drinking remains largely under-recognised (10) and has not been a target of breast cancer prevention efforts.

Alcohol brief interventions are recommended in the recently updated Australian guidelines for the treatment of alcohol use problems (11), and there is an expansive literature demonstrating their effectiveness in improving alcohol literacy and reducing consumption when delivered in general practice settings (12, 13). However, multiple barriers to their implementation remain (e.g. longer consultations are not adequately remunerated, training is suboptimal, and treatment services are not readily available when advice or referral is required), and there has been a call for other health profession involvement in responding to harmful alcohol consumption and leading clinical practice change to reduce alcohol-related harms (14). Population-based breast screening programs are uniquely positioned to provide timely and targeted health information and behaviour change strategies to improve women's alcohol literacy and reduce consumption; the screening appointment can act as a window of opportunity to increase engagement with breast cancer risk reduction information. With approximately 43 million women participating in breast screening each year in Australia, the US and UK alone, this setting has potential for extensive reach.

We recently completed a world-first trial (N=558), funded by VicHealth and the Eastern Health Foundation, supported by Maroondah BreastScreen (trial site) and BreastScreen Victoria, and approved by the Eastern Health Human Research Ethics Committee (LR19/011/50551), to test the effectiveness of a prototype of an electronic alcohol brief intervention (Health4Her; researcher-

administered screening alcohol questions, intervention activated by the researcher for the participant to view on an iPad alone). The electronic alcohol brief intervention model was chosen to minimise disruption to service workflow and need for human resource to implement within the busy breast screening environment. In this trial, participants reported poor alcohol literacy (4 in 5 did not have knowledge of the alcohol-breast cancer link) and a desire for more information. The Health4Her intervention was found to be highly acceptable to breast screening service consumers. For the primary outcome, there were significant increases in the proportion of participants accurately identifying alcohol as a clear breast cancer risk factor from baseline to 4-weeks in intervention (OR=41.82, 95% CI=17.76, 98.49, $p<0.001$) and control (OR=4.92, 95% CI=2.75, 8.79, $p<0.001$) arms, with a significantly greater increase in the intervention arm ($p_{\text{arm} \times \text{time}} < 0.001$) (Findings are currently under peer-review for publication). BreastScreen staff were highly supportive of the Health4Her intervention as part of routine care, however, the manually delivered intervention, dependent on dedicated human resource to administer, was considered unviable to implement in practice.

As such, the overall aim of this study is to i) collaboratively design an automated alcohol brief intervention with women who participate in breast screening, ii) examine its effects on drinking intentions and alcohol consumption among women attending breast screening service for routine mammography and iii) understand the factors affecting intervention implementation using mixed-methods program evaluation.

